### 8.2.3 Time Period for Adverse Events

For purposes of this study, events that occur following randomization through 14 days after study drug initiation or until hospital discharge (whichever comes first) will be reported as adverse events. ED revisits and hospital admissions will be tracked through 28 days following hospital discharge. Specifically, events that occur following parental permission to participate in the study, but prior to actual randomization, are not adverse events. These should be recorded as baseline conditions.

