#### 4.5.1 Schedule of Events

The Schedule of Events (table 3) summarizes data collection for each time point in the study.

Table 3: Schedule of Events

	Screening	Pre-Dose 	Day 1 	Day 2 	Day 3-7 	Day 8 or Discharge 	Day 14 and/or Day 28 
I/E	X	X					
Demographics and Genotype		X					
Study Treatment Assignment		X					
Medical History	X	X					
Pain Crisis Start Date and time a		X					
Time of Last IV opioid/Pain Crisis End date and time b						X	
Number of ED visits/hospitalizations in last year (excluding current)		X					
ED admission information		X					
Time of IV placement		X					
Conmeds		X	X	X	X	X	
CMP d	X d	X d		X d			
BHCG e		X					
Research Labs		X		X		X	
Vital Signs f	X		X	X	X	X	
Pain Score f	X		X	X	X	X	
PROs (PROMIS/Peds) QL/ASCQ-Me (adults)		X (within 12 hours)					X
MQS Score		X	X	X	X	X	X
Symptoms Questionnaire g		X		X	X	X	X
Opioid Monitoring h	X	X	X	X	X	X	X
Maintenance Fluid Monitoring h		X	X	X	X	X	
AE i		X	X	X	X	X	X
SAE i		X	X	X	X	X	X
Study Drug Administration j			X	X	X	X	

Continued on next page...

Table 3 – *continued from previous page...*

---

- 1 – Predose is all information that is collected before the start of study drug.
- 2 – Day 1 is from the start of Study Drug to midnight of the day study drug is started. Pre-Dose and Day 1 may occur on the same day.
- 3 – Day 2 is the day after study drug is administered (starting at midnight of the day the study drug is started).
- 4 – Individual patient hospitalization duration will vary. Patients may be discharged at any time between Day 1 through Day 7.
- 5 – Day 8 is the day that the last dose #21 will be given for patients who have not yet been discharged.
- 6 – If patients are not discharged by Day 8, an AE/SAE review will occur daily until Day 14. ED revisits and hospital admissions will be captured through 28 days following hospital discharge.
- a – Pain Crisis start date/time is defined as the date/time the patient started experiencing pain (this could be before ED visit).
- b – Pain crisis end date/time is defined as the date/time of last dose of parenteral opioid delivery.

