- c – Research labs: will be obtained with routine daily blood draws whenever possible and may be drawn on days when the research and clinical team suspect the patient may be discharged to avoid multiple venipunctures. In the event the patient is not discharged on that date, discharge labs should be drawn again prior to discharge. Baseline labs to be drawn before the start of study drug.
- d – Screening CMP from a clinically ordered CMP or the last CMP in the medical record within the last 12 months will be reviewed. If there are any values within higher than protocol defined cut offs for study drug withdrawal, then a CMP is to be drawn and reviewed prior to randomization. For participants with normal past CMP, a CMP will be done on day 2.
- e – Pregnancy test obtained at Pre-Dose for females 13 years and older.
- f – The first set of Vital Signs (including oxygen saturation) and Pain scores will be captured when the patient first presents to the Emergency Department. The highest and lowest pain scores will be recorded from Day 1 through Day 8 (or within 6 hours of Discharge). The first set of vitals signs after 6 am will be collected up until Day 8/Discharge, whichever comes first. Ensure oxygen saturation is captured at Pre-Dose and within 6 hours of Discharge.
- g – Symptoms Questionnaire will be completed daily through Day 14 or Discharge.
- h – Use of Parenteral Opioids will be documented every shift by nursing staff per standard protocol, including opioids delivered by the PCA device as well as any intravenous, intranasal and/or oral opioids used. Data on daily opioid use will be collected and recorded.
- i – AEs and SAEs will be monitored daily through discharge or through 14 days of hospitalization; Return ED visits and hospitalizations will be followed for 28 days after hospital discharge.
- j – Patients will be randomized within 12 hours of their initial dose of parenteral opioid in the ED or ward and Arginine will be administered TID.

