**Specific Aim 2: To determine the safety profile of IV L-arginine in the treatment of acute VOE in children with SCD.**

Analysis of safety outcomes (acute chest syndrome, requirement of blood transfusion, oxygen use, return visits, and clinical deterioration) will be conducted using Mantel-Haenszel chi-square tests, stratified by clinical center and age group.

Summaries of incidence rates (frequencies and percentages), intensity, and relationship to study of individual Adverse Events (AEs) by System Organ Class and Preferred Term (MedDRA) will be prepared. All AEs beginning after randomization through 14 days or until hospital discharge (whichever comes first) will be included. ED revisits and hospital admissions will be tracked through day 28 after hospital discharge. The occurrence of any adverse event will be considered as a dichotomous outcome and will be compared between groups using a Mantel-Haenszel test, stratified by clinical center and age group. Adverse events will be coded using the latest version of the Medical Dictionary for Regulatory Activities (MedDRA).

**Specific Aim 3: (Exploratory) 3a. To characterize alterations in the arginine metabolome and mitochondrial function in children with SCD and VOE, and evaluate how it is impacted by IV arginine therapy.**

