### 8.2.1 Definition of Adverse Event and Serious Adverse Event

**Adverse Event (AE)** means any untoward medical occurrence associated with the use of an intervention in humans, whether or not considered intervention-related (21 CFR 312.32 (a)). An event constitutes a disease, a set of related signs or symptoms, or a single sign or symptom.

**Serious Adverse Event (SAE):** A serious adverse event (SAE) for this population is an adverse event that:

- results in death; or
- is life-threatening (the patient was, in the view of the site investigator, in immediate danger of death from the event as it occurred); or

- requires inpatient hospitalization or prolongs an existing hospitalization; or
- results in persistent or significant disability or incapacity; or
- results in congenital anomaly/birth defect; or
- any other event that, based upon appropriate medical judgment, may jeopardize the subject's health and may require medical or surgical intervention to prevent one of the other outcomes listed in this definition.

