#### **8.2.4 Data Collection Procedures for Adverse Events**

After patient randomization all adverse events (including serious adverse events) will be recorded according to relatedness, severity, and expectedness, as well as their duration and any treatment prescribed. Any medical condition present at the time of randomization, recorded in the patients baseline history at study entry, which remains unchanged or improves (unless the clinician feels it is clinically relevant), will not be recorded as an adverse event at subsequent evaluations. However, worsening of a medical condition that was present at the time of randomization will be considered a new adverse event and reported.

Abnormal laboratory values that are clinically significant will be recorded as adverse events and the site investigator will assess the severity and relationship to the study. Laboratory values that are abnormal at the time of randomization and that do not worsen will not be recorded as adverse events.

Adverse events will be coded using the MedDRA coding vocabulary. Coding will be done centrally at the Data Coordinating Center as this requires specific training.

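### AE and SAE reporting ends at discharge or day 14, while the 28-day follow-up names no vital-status check and no rule for assessing readmissions as SAEs

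*Combined protocol and SAP*

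**What the plan says.** Four places set the reporting window:

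- Section 8.2.3: events from randomization up to 14 days after the first study dose "or until hospital discharge (whichever comes first) will be reported as adverse events". The next sentence adds that "ED revisits and hospital admissions will be tracked through 28 days following hospital discharge".
- Section 5.1, Specific Aim 2, uses the same window for analysis: "All AEs beginning after randomization through 14 days or until hospital discharge (whichever comes first) will be included".
- Table 3, note i, names SAEs as well: "AEs and SAEs will be monitored daily through discharge or through 14 days of hospitalization". After that it mentions only return visits and hospitalizations, for 28 days.
- Table 3, note 6: for children not discharged by Day 8, "an AE/SAE review will occur daily until Day 14".

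Section 8.2.1 defines an SAE as an adverse event with a serious outcome. Death is one criterion; another is that the event "requires inpatient hospitalization or prolongs an existing hospitalization". Section 8.2.6 requires sites to report SAEs to the Data Coordinating Center within 24 hours, and the medical monitor assesses the SAEs that sites report. The Synopsis puts participant duration at 28 days after discharge.

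Two places are looser. Section 8.2.4 says "After patient randomization all adverse events (including serious adverse events) will be recorded", with no end date in that sentence. Table 3, as it reads in the extracted text, marks the AE and SAE rows under "Day 14 and/or Day 28".

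**The concern.** The trial runs two post-randomization safety systems with no stated link between them. One is AE/SAE reporting, with investigator assessment of relatedness and expectedness and review by the medical monitor. The other is a 28-day record of revisits and admissions. For most children the first closes at discharge, just as the second becomes the only source of information.

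A readmission for a serious new event shortly after discharge would be tracked as a return visit, but no sentence requires anyone to ask whether it is an SAE. A death at home generates neither a revisit nor an admission, so neither system is designed to find it. Safety is Specific Aim 2, and the Abstract presents the trial as a source of data for regulatory approval. Early post-treatment serious events should therefore be identified as such and not left to be inferred from visit counts.

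**Working it through.** The documents give no figure to reproduce here, so the check sets the provisions side by side and then sizes the gap.

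**1. Does the window apply to SAEs?** Yes. Section 8.2.1 makes an SAE a kind of adverse event, so it inherits the window in Section 8.2.3, and note i names SAEs directly. For a stay longer than 14 days the earlier limit applies, so new-event reporting stops at day 14 while the child is still in hospital.

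**2. What is collected after discharge?** Section 5.1, Section 8.2.3 and notes 6 and i all name ED revisits and admissions only. No section names a vital-status item. Death appears in Section 8.2.2 as an outcome of an adverse event that has already been recorded.

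**3. Is there another route to individual review?**

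- Unanticipated problems (Section 8.2.5): no end date, a 24-hour report, and a role for the medical monitor. The event must be unexpected, at least possibly related, and suggest greater risk than was known. Table 5 lists stroke, sepsis and pulmonary embolism as expected, and Table 4 lists cardiac and respiratory arrest. Such events could miss this route.
- Follow-up of SAEs (Section 8.2.7): up to 12 months from the last dose, but only for SAEs still unresolved at discharge or study termination.
- Return visits as a safety outcome (Section 1.4, Aim 2, and Section 5.1): compared by arm as counts, which is not case review.

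**4. Share of participation covered by AE/SAE reporting.** For discharge on day *d*, the share is min(*d*, 14) / (*d* + 28):

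| Discharge day | Covered days / total days | Share |
|---|---|---|
| 3 | 3 / 31 | 10% |
| 7 | 7 / 35 | 20% |
| 8 | 8 / 36 | 22% |
| 14 | 14 / 42 | 33% (the maximum) |
| 20 | 14 / 48 | 29% |

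**5. Readmissions within 72 hours.** Inputs: N = 360 (Section 1.5). Section 2.8 gives 6% in its report on an earlier phase 2 protocol with 83 children, and 20% as a literature figure. Expected count = N × rate, with a binomial 95% range:

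- 360 × 0.06 = 21.6, range 13 to 31 (about 11 per arm if equal).
- 360 × 0.20 = 72, range 57 to 87 (36 per arm).

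These ranges treat the rate as known. If 83 is its denominator, the 6% itself rests on about five children (0.06 × 83 = 4.98).

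**6. Deaths after discharge.** The documents give no rate, so this is assumption only. The chance of at least one such death in 360 is 1 − (1 − *q*)^360: 16% at *q* = 0.05%, 30% at 0.1%, 66% at 0.3% and 84% at 0.5%.

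**The case against.** The strongest reply is that the window is deliberate and that other provisions cover what matters. The window is stated in much the same form in several places. Dosing ends at discharge or after 21 doses, so the window roughly tracks exposure, and the DSMB approves the final protocol. Readmissions are visible because they are a formal outcome compared by arm.

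A reader might go further than the documents allow in four ways:

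- *That a post-discharge death is not captured at all.* A death during a tracked revisit or admission would probably surface. So would one from an SAE already open at discharge, or one that qualifies as an unanticipated problem. Data-field and safety-reporting detail may also sit in the EDC, worksheets and manual of operations, which are not part of these documents.
- *That FDA reporting would miss these events.* Section 8.2.6 has the IND sponsor report study-related, unexpected serious reactions with no stated time limit.
- *That about 22 SAEs would go unreported.* Section 2.8 gives no reasons for re-hospitalization. Section 8.2.1 requires an adverse event first, and under Section 8.2.4 a condition present at randomization that is unchanged or improved is generally not recorded as one. Worsening of such a condition is, so a return for pain needs a judgement.
- *That Table 3 plainly contradicts the text.* Note 6 is attached to that column and can be read as limiting the AE/SAE marks to Day 14. The column positions may also be an artefact of reading the PDF.

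These points remove the absolute claims. They do not supply a rule for screening readmissions or a check of vital status. The open-ended sentence in Section 8.2.4 also leaves sites free to read the window differently.

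**Conclusion.** The gap is real but narrower than total loss of post-discharge events. Followed as written, the protocol does not systematically ascertain a new-onset death outside hospital. It also does not require individual review of a serious readmission judged expected or unrelated, or reporting of a new event after day 14 in a child still in hospital.

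For the first 72 hours after discharge, about 22 children at the 6% rate, or 72 at the 20% rate, would be candidates for SAE assessment. How many would prove to be SAEs cannot be said. Both counts assume that the quoted rates carry over to this trial. Full 28-day counts and deaths cannot be estimated from the documents.

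No sample size, power or significance level is affected. This is a cheap improvement to safety capture, not a flaw in the efficacy design.

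**What to change.** - In Section 8.2.3 and note i to Table 3, add vital status to the existing 28-day follow-up.
- In the same places, state that any death, and any revisit or admission in that period that is an adverse event meeting Section 8.2.1, goes through SAE reporting under Section 8.2.6. This should also cover children still in hospital after day 14.
- Pre-list readmissions for uncomplicated pain for periodic rather than 24-hour reporting, to contain the load.
- Align the analysis window in Section 5.1, give the recording sentence in Section 8.2.4 an end date, and make the AE and SAE marks in the last column of Table 3 agree with the chosen window.

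The cost is protocol wording, one follow-up item and some extra SAE forms. Sites already track the revisits and admissions, so the added work is assessing them. The number of forms depends on how many readmissions prove to be adverse events meeting the definition, which the documents do not show.

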#### **8.2.4 Data Collection Procedures for Adverse Events**

After patient randomization all adverse events (including serious adverse events) will be recorded according to relatedness, severity, and expectedness, as well as their duration and any treatment prescribed. Any medical condition present at the time of randomization, recorded in the patients baseline history at study entry, which remains unchanged or improves (unless the clinician feels it is clinically relevant), will not be recorded as an adverse event at subsequent evaluations. However, worsening of a medical condition that was present at the time of randomization will be considered a new adverse event and reported.

Abnormal laboratory values that are clinically significant will be recorded as adverse events and the site investigator will assess the severity and relationship to the study. Laboratory values that are abnormal at the time of randomization and that do not worsen will not be recorded as adverse events.

Adverse events will be coded using the MedDRA coding vocabulary. Coding will be done centrally at the Data Coordinating Center as this requires specific training.

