## 4.5 Data Collection

**Primary Outcome Measure:** *Time-to-crisis resolution*, defined as the time in hours from study drug delivery to time of last dose of parenteral opioid delivery.

- Data being collected: date and time of first study drug administration and last IV opioid treatment

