**Expected:** An event is considered expected if it is known to be associated with the underlying condition or is related to the study intervention and is mentioned in the protocol, informed consent, or other study documents. An event may be expected despite the study subjects clinical state immediately prior to the event.

**Unexpected:** An event is considered unexpected if there are no prior data linking this event with either the condition or intervention under study or an event that occurred unexpectedly in the course of treatment.

Expected complications of opioid administration and sickle cell anemia are summarized in Tables 4 and 5. Other expected adverse events are reactions known to occur with arginine administration, specifically nausea, vomiting, headache, flushing, warmth at the infusion site.

Table 4: Expected Adverse Events Related to Opioid Administration

Anorexia	Headache
Apnea	Hypotension
Biliary tract pressure	Miosis
Blurred vision	Nausea
Bradycardia	Palpitations
Bruising	Pruritus
Cardiac arrest	Rash
Confusion	Respiratory arrest
Cramps	Respiratory depression
Diaphoresis	Sedation
Diplopia	Shock
Dizziness	Tinnitus
Drowsiness	Urinary retention
Euphoria	Urticaria
Flushing	Vomiting

Table 5: Expected Adverse Events Related to Sickle Cell Disease Progression

Angioedema	Leukocytosis
Aplastic crisis	Meningitis
Aplastic crisis/anemia	Metabolic acidosis
Arthralgia	Osteomyelitis
Appendicitis	Pyelonephritis
Bone Infarction	Pain, joint
Cardiomegaly	Pain, long bone
Cerebrovascular accident	Pain, severe abdominal
Cholecystitis, hepatic sequestration	Priapism

*Continued on next page...*

Table 5 – *continued from previous page...*

Cranial nerve palsy	Pulmonary embolism
Decreased kidney function	Pulmonary hypertension
Decreased lung function	Pulmonary parenchymal infiltrates on CXR
Delayed growth/puberty	Pneumonia
Depresses ESR	Rhabdomyolysis
Fever	Renal Failure
Headache	Renal Insufficiency/albuminuria
Hematuria	Renal papillary necrosis
Hemiplegia	Reticulocytosis (10%–20%)
Hemolysis	Retinal disease
Hepato/splenomegaly	Retinal hemorrhage
Hyperplastic bone marrow	Skin ulcers
Hyposthenuria	Splenic sequestration
Hypoxia (PO 2 < 85 mm Hg)	Stroke
Hyperkalemia	Sepsis
Hypotension	Upper respiratory infection
Infection, pneumococcal	Urinary tract infection

**Treatment or Action Taken:** For each adverse event, the site investigator will record whether an intervention was required:

- Medical or surgical procedure

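### Worsening of the index pain crisis counts as an adverse event and is not separated in the any-AE comparison, so that pooled test can be diluted or tilted in arginine's favour

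*Combined protocol and SAP*

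**What the plan says.** Section 8.2.4 sets two rules for a condition already present at randomization. If it worsens, the rule is that "worsening of a medical condition that was present at the time of randomization will be considered a new adverse event and reported". A condition "which remains unchanged or improves (unless the clinician feels it is clinically relevant), will not be recorded as an adverse event at subsequent evaluations". The section does not define worsening.

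The inclusion criteria (1.6) require sickle cell pain treated with parenteral opioids, so every participant has the index vaso-occlusive episode (VOE) at randomization. No section exempts it from the worsening rule. Table 5 in 8.2.2 lists pain terms, such as "Pain, long bone", among the expected AEs of sickle cell disease. Under 8.2.1 an AE is serious if it "requires inpatient hospitalization or prolongs an existing hospitalization", again with no exemption for the VOE.

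For the analysis, section 5.1 (Specific Aim 2) states: "The occurrence of any adverse event will be considered as a dichotomous outcome and will be compared between groups using a Mantel-Haenszel test", stratified by center and age group. No event type is set aside. The same section also plans "Summaries of incidence rates (frequencies and percentages), intensity, and relationship to study of individual Adverse Events (AEs) by System Organ Class and Preferred Term", and separate Mantel-Haenszel tests of five named outcomes: acute chest syndrome, transfusion, oxygen use, return visits and clinical deterioration. It specifies no between-arm test of SAEs.

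**The concern.** Hypotheses 1 to 3 expect arginine to improve pain; Hypothesis 4 expects a safety profile similar to placebo. The any-AE comparison is the only formal test of AEs overall, and it counts worsening of the pain that the drug is meant to treat. Two things follow.

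- **Dilution.** Pain events that occur in both arms raise both any-AE rates and shrink the difference caused by other events.
- **Bias towards arginine.** If arginine reduces pain worsening, it removes events from its own arm. That offsets an excess of other AEs, or makes arginine look safer when the other AEs are equal.

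This matters most for events that have no test of their own. The arginine reactions in 8.2.2 (nausea, vomiting, headache, flushing, warmth at the infusion site) and the acidosis and hyperkalemia discussed in 7.4 are not among the five named outcomes. Unless they appear as clinical deterioration, they reach a formal comparison only through the any-AE test. Because worsening is undefined, sites may also record it differently.

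**Working it through.** **Inputs from the documents.** 180 per arm (5.2), equal allocation (4.2), two-sided tests (section 5). The 180 reproduces: 166 × 1.08 = 179.3, rounded up to 180.

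**Assumptions.** The documents give no AE rates and no significance level for the safety tests. I assume 0.05, independence of worsening and other AEs, and no stratification. Let t be the proportion with any other AE and w the proportion with index-VOE worsening; P is placebo and A is arginine. I take tP = 20% and tA = 30%, a real excess of 10 points, and vary w.

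**Formulas.**

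- Any-AE rate: p = 1 − (1 − t)(1 − w).
- Power = Φ[(|pA − pP| − 1.96 × se0) / se1], with se0 = √[2p̄(1 − p̄)/180], p̄ the mean of the two rates, and se1 = √{[pP(1 − pP) + pA(1 − pA)]/180}.

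**Without worsening events.** p̄ = 0.25, se0 = √(2 × 0.25 × 0.75/180) = 0.0456 and se1 = √[(0.16 + 0.21)/180] = 0.0453. Power = Φ[(0.10 − 1.96 × 0.0456)/0.0453] = Φ(0.23) = 59%.

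**With worsening events.** For example, at 20%/10%: pP = 1 − 0.8 × 0.8 = 36% and pA = 1 − 0.7 × 0.9 = 37%.

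| Worsening, P/A | Any AE, P | Any AE, A | Difference (points) | Power |
|---|---|---|---|---|
| none | 20.0% | 30.0% | 10.0 | 59% |
| 5%/5% | 24.0% | 33.5% | 9.5 | 51% |
| 20%/20% | 36.0% | 44.0% | 8.0 | 34% |
| 10%/5% | 28.0% | 33.5% | 5.5 | 20% |
| 20%/10% | 36.0% | 37.0% | 1.0 | about 5% |
| 30%/20% | 44.0% | 44.0% | 0 | excess erased |
| 40%/25% | 52.0% | 47.5% | −4.5 | sign reversed |

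At 20%/10% the formula gives 4% in the direction of harm; with the opposite tail, about 5% of trials are significant in either direction.

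**When can the sign reverse?** Setting pA < pP gives wA < 1 − 0.8(1 − wP)/0.7. The limit is 8.6% when wP is 20%, 20.0% when wP is 30% and 31.4% when wP is 40%. At wP = 10% it is 1 − 0.72/0.70 = −2.9%, which no rate can meet. So with placebo worsening of 10% or less the excess only shrinks.

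**No true difference in other AEs.** With t = 20% in both arms and worsening at 20%/10%, any AE is 36% v 28%. Then p̄ = 0.32, se0 = 0.0492, se1 = 0.0490, and Φ[(0.08 − 1.96 × 0.0492)/0.0490] = Φ(−0.33) = 37%. In about 37% of such trials the test would call the arms different, with arginine lower, through pain events alone.

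**Other assumed rates.** With other AEs at 40% v 52%, power is 63% without worsening events and 58% with worsening at 5% in both arms (43.0% v 54.4%). If worsening is rarely recorded and equal between arms, the loss is small.

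**The case against.** The strongest reply is that the plan does not rest its safety conclusion on this one test. Individual AEs are tabulated by MedDRA term with intensity and relationship, five outcomes are tested separately, the medical monitor assesses every SAE (8.2.6), and the DSMB reviews all AEs. An excess of vomiting or acidosis would be visible there. Central MedDRA coding would also let an analyst look at pain terms separately. All of this stands, and it limits the point to the pooled test.

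Four stronger readings might be inferred, and the documents do not support them.

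- **The any-AE test absorbs the efficacy outcome.** The primary outcome is "defined as the time in hours from study drug delivery to time of last dose of parenteral opioid delivery". A crisis that resolves slowly without worsening is ordinarily not an AE under 8.2.4, so its duration is not counted again as safety.
- **Every rise in a pain score is an AE.** Section 8.2.4 speaks of worsening of a condition and gives no threshold. Table 5 is a list for judging expectedness; it shows that pain can be reported as an AE, not that each fluctuation must be.
- **A real toxicity would be hidden or reversed.** Masking affects one test among several, and reversal needs frequent worsening and a large benefit.
- **A formal SAE comparison is distorted.** None is planned. The route from worsening to an SAE through a prolonged stay exists, but it affects reporting, not a stated test.

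Two further replies have some force. A non-significant difference never establishes similarity, so Hypothesis 4 would not be settled by this test in any case. And section 9 refers to a manual of operations covering safety reporting, which may say how index pain is recorded; it is not among the documents. Neither reply changes what 5.1 pools.

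**Conclusion.** The point holds as a limited defect in one stated test. Under 8.2.4 worsening of the index VOE is an AE, and 5.1 pools it with everything else, so the any-AE comparison can lose power or lean towards arginine. The direction is predictable if arginine works as hypothesized.

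The size is unknown, because it depends on AE rates that the documents do not give. In the main illustration (other AEs 20% v 30%), the cost runs from a modest loss of power, 59% to 51%, when worsening is rare and equal, to complete cancellation when worsening is 30% on placebo and 20% on arginine. The figures also rest on independent events, a 0.05 level and no stratification. The safety analysis as a whole is not invalidated. This is a cheap improvement worth making before unblinding.

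**What to change.** - **Section 8.2.4:** state what counts as worsening of the index VOE for AE recording, and add a flag for such events on the AE form. Prolongation without worsening needs no flag, since it is ordinarily not an AE.
- **Section 5.1:** report the any-AE comparison twice, once with all events and once excluding flagged index-VOE worsening. Tabulate SAEs both ways, descriptively.

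Nothing is removed from collection or reporting, and new complications such as acute chest syndrome stay counted in both versions. The cost is one tick-box, a sentence or two in each section and one extra table. The downside is that sites must judge whether worsened pain belongs to the index crisis; they do so while blinded, so errors should not favour either arm systematically.
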